#### 8.2.1. Inclusion Criteria

Patients must meet each of the following inclusion criteria to be eligible for inclusion in the study:

1. Diagnosed AS patients.
2.  $\geq 18$  years old.
3. Did not receive previous biological treatment for any reason.

### **8.2.2. Exclusion Criteria**

Patients meeting any of the following criteria will not be included in the study:

1. Patients previously or currently treated with other biological therapies.
2. Use of etanercept for less than 1-year duration.

### **8.3. Data Sources**

Patients will be identified from the rheumatology patient registry with rheumatoid arthritis and will obtain information on patient demographics (age, gender), education level (years), present smoking status, disease duration (years), current steroid therapy (yes/no), baseline bath ankylosing spondylitis disease activity index (BASDAI), Bath Ankylosing spondylitis functional index (BASFI), human leukocyte antigen B27 (HLA-B27), anticitrullinated protein antibody (anti-CCP) status.

Primary Outcomes: Disease activity Index BASFI and BASDAI from the last follow-up visit.

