## NON-INTERVENTIONAL (NI) STUDY PROTOCOL

### Study Information

Title	Clinical Outcomes of Early Versus Delayed Management of Iraqi Patients With ankylosing spondylitis (AS) With Etanercept
Protocol number	B1801415
Protocol version identifier	3.0
Date	29 July 2021
Active substance	Etanercept
Medicinal product	Etanercept
Research question and objectives	Many publications found that the early initiation of biological treatment had positive impact on patients' response to the treatment regimen, and with this Real World Data (RWD), our objective is to evaluate the impact of early initiation of etanercept on patient-response compared to delayed introduction of biological treatment.
Author	PPD – MD, M.Sc. PPD Pfizer Inc. – Iraq
This document contains confidential information belonging to Pfizer. Except as otherwise agreed to in writing, by accepting or reviewing this document, you agree to hold this information in confidence and not copy or disclose it to others (except where required by applicable law) or use it for unauthorized purposes. In the event of any actual or suspected breach of this obligation, Pfizer must be promptly notified.	

PFIZER CONFIDENTIAL

A thick black horizontal bar redacting sensitive information.

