## 6. RATIONALE AND BACKGROUND

In the past 1–2 decades, treatment paradigms in Ankylosing Spondylitis (AS) have shifted dramatically from initial treatment with nonsteroidal anti-inflammatory drugs (NSAIDs), followed by the cautiously progressive addition of disease-modifying antirheumatic drugs (DMARDs), to the current treatment approach of the aggressive initiation of DMARD therapy soon after the diagnosis of AS has been made. This change in AS management results from increasing data supporting improved prognosis and outcomes with the initiation of DMARD therapy early in the course of symptomatic disease. Since the goals in AS management include not only disease remission but also improved functional status, which is strongly associated with radiographic joint damage, an understanding of the impact that the initiation of appropriate treatment during early AS has on these outcomes is essential.

Accurate diagnosis of early AS begins with clear definitions of AS, as there is considerable variability in the literature regarding the time frame defining early AS. Previous intervention studies in early AS have included early AS as disease duration from 3 months to 3 years; however, with the knowledge of improved outcomes with earlier treatment in AS, it becomes clear that a shorter time interval for classification of early rheumatoid arthritis (RA) is clinically significant. Due to the wide range of definitions of early AS presented in the literature, it is difficult to characterize the specific time frame that defines early AS.

Multiple studies have evaluated the benefits of early treatment of AS, including several that have evaluated the impact of early DMARD treatment on successful response to therapy. In particular, a meta-analysis of ~1,400 AS patients from 14 randomized controlled trials identified that one of the strongest predictors of response to therapy was a shorter disease duration at the time of treatment initiation.

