## 8. RESEARCH METHODS

### 8.1. Study Design

- **Retrospective analysis** of patients with AS that received etanercept from Baghdad teaching hospital (Rheumatology center) from August 2012 until March 2020 (inclusion and exclusion criteria will apply for selecting patients).
- **Primary objective:** determine the clinical impact of early referral for management in patients with AS compared to delayed management.
- **Secondary objective:** determine the influence of early referral on the response to biological treatment.

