### 8.2. Setting

#### Patients and Methods

Data will be collected from the Baghdad Teaching Hospital registry. The rheumatology patient registry is a prospective longitudinal multicenter cohort initiated in 2012. It captures all patients treated with biologic therapies managed in the rheumatology department. The decision to initiate and maintain the treatment is guided by the American College of Rheumatology (ACR) recommendations.

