#### Study population

Patients will be included in the study if they met the American College of Rheumatology/The European League Against Rheumatism (EULAR) 2019 criteria for AS, with at least 1 year of follow up after starting their first biologic therapy.

Exclusion criteria: patients previously or currently treated with other biological therapies.

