### **8.4. Study Size**

There is no pre-identified study size. All patients that meet the inclusion/exclusion criteria will be entered into the study.

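### Does naming rheumatoid arthritis in Section 8.3, and leaving methotrexate off its variable list, put the cohort or the regression at risk?

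*Combined protocol and SAP*

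**What the plan says.** Section 8.3 (Data Sources) opens with "Patients will be identified from the rheumatology patient registry with rheumatoid arthritis". It then lists what will be obtained: demographics, education, smoking, disease duration, steroid use, baseline BASDAI and BASFI, HLA-B27 and anti-CCP. Methotrexate is not listed.

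Elsewhere the disease is AS:

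- Title: "Clinical Outcomes of Early Versus Delayed Management of Iraqi Patients With ankylosing spondylitis (AS) With Etanercept".
- Section 8.1: a retrospective analysis "of patients with AS that received etanercept from Baghdad teaching hospital".
- Section 8.2, Study population: "criteria for AS, with at least 1 year of follow up after starting their first biologic therapy".
- Section 8.2.1, first inclusion criterion: "Diagnosed AS patients".
- Section 8.6: the regression is for treatment response in AS patients.

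Section 8.2 says of the registry: "It captures all patients treated with biologic therapies managed in the rheumatology department". Section 8.4 says: "All patients that meet the inclusion/exclusion criteria will be entered into the study". Section 8.6 names methotrexate (yes/no) among the baseline variables for the stepwise linear regression. Section 8.7 gives quality control as not applicable.

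**The concern.** The disease term in Section 8.3 stands in the sentence that says which records to pull. The registry holds every biologic-treated patient in the department, so choosing the disease is a real selection step. Someone who built the query from that sentence alone would retrieve the wrong patients, and a later AS screen cannot bring back patients who were never retrieved.

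The methotrexate gap is a separate matter. If only the Section 8.3 items were extracted, the regression could not consider a variable that Section 8.6 names, and the adjusted effect of disease duration would be estimated without it. No quality-control step is planned. Data collection was due to end on 01 October 2020, before this version of 29 July 2021. At stake would be the wrong cohort in the worst case, or one missing candidate covariate in the milder case.

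**Working it through.** No sample size, power or effect figure is given, so there is nothing to recompute. The check sets the sections side by side.

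**1. Disease term.** Rheumatoid arthritis is spelled out three times in the supplied text: in the abbreviation list, in Section 6 and in Section 8.3. The Section 6 instance, "a shorter time interval for classification of early rheumatoid arthritis (RA) is clinically significant", falls in the middle of an argument about early AS and is plainly a slip. The Section 8.3 instance fits the same explanation, because its own sentence goes on to collect BASDAI and BASFI, both of which carry ankylosing spondylitis in their names. The phrase could instead be read as describing the registry, but that would conflict with Section 8.2, where the registry covers all biologic-treated patients in the department. Neither reading makes rheumatoid arthritis the study disease.

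**2. Which rule decides entry.** Section 8.2.1 requires an AS diagnosis, and Section 8.4 enters those who meet the criteria. Under the written rules:

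| Registry patient | Meets 8.2.1, criterion 1 | Can enter |
|---|---|---|
| AS | yes | yes, if the other criteria are met |
| Rheumatoid arthritis without AS | no | no |

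The term in Section 8.3 therefore cannot admit an ineligible patient. It could only lose eligible ones, and only if the query were run literally. Assuming that few patients carry both diagnoses (the documents give no figure), a literal query screened for AS would return almost nobody. A nearly empty AS cohort could not go unnoticed.

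**3. Variable lists.** Section 8.6 baseline entries, with demographics counted as one:

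| Section 8.6 entry | In the Section 8.3 list |
|---|---|
| Demographics | yes |
| Disease duration | yes |
| Methotrexate | no |
| Current steroid | yes |
| Baseline BASFI | yes |
| Baseline BASDAI | yes |
| HLA-B27 | yes |
| Anti-CCP | yes |
| Present smoking | yes |

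That is 9 entries, of which 8 match and 9 − 8 = 1 does not.

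**4. Is the Section 8.3 list complete?** Section 8.2.2 excludes patients with less than one year on etanercept, and Sections 8.2.1 and 8.2.2 both turn on prior biologic use. Neither duration of etanercept nor biologic history is in the Section 8.3 list. An extract confined to that list could not have been used to apply the eligibility criteria, so the list is not exhaustive. The absence of methotrexate from it does not show that methotrexate was not to be extracted. Section 8.6 belongs to the same protocol and specifies the variable and its coding.

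**5. Who fills the gap.** Under Section 8.5 the rheumatology center at the hospital that holds the registry analyzes the data. Its staff work from the whole protocol, and the title, design, criteria and outcome indices all name AS.

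**The case for a change.** The strongest case for acting is that the error sits in an operative sentence, that Section 8.7 plans no quality control, and that Section 8.3 introduces its list with no wording to suggest it is only illustrative. A covariate that was considered and dropped differs from one that was never available. Since collection was due to end before this version, only a statement in the report would tell a reader what was pulled.

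Part of this stands. The wording is wrong, the lists differ by one item, and a report that states its disease filter and extracted variables is better documented than one that does not.

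The rest does not carry over to the plan. It is not true that no planned step would catch the disease term, because applying the AS inclusion criterion is such a step. The completeness of the list is contradicted by the protocol's own eligibility needs. The documents give no figure for methotrexate use and nothing to link it to disease duration or response, and a stepwise procedure might drop it in any case. Rewording Section 8.3 in July 2021 would not alter an extraction planned to finish almost ten months earlier, and nothing in the documents suggests that the extraction was wrong.

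**Conclusion.** No change to the plan follows. The disease name in Section 8.3 is a clerical slip with only one workable reading, since AS governs entry through Sections 8.2.1 and 8.4. The methotrexate omission is one item of nine missing from a list that is evidently incomplete, and Section 8.6 supplies the instruction itself. The analysts at the hospital center can be expected to fill both gaps sensibly.

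The effect on the cohort or the estimate cannot be sized from the documents. It is nil if the registry was queried for AS and methotrexate was extracted. This conclusion rests on two assumptions: that the center read the protocol as a whole, and that few patients carry both diagnoses, so that a literal query would have exposed itself. Correcting the disease term and aligning the two lists would be editorial tidying, and reporting the filter and variables used would be documentation. Neither would alter the population, the model or the interpretation.

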#### Hypothesis

There is no difference in response between early and delayed referral to biological treatment.

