### **8.6. Data Analysis**

All covariates will be summarized to get information about frequency distribution and mean, median or standard deviation. Numbers and percentages will be provided for categorical variables when performing descriptive analysis. Means, medians, standard deviations, or interquartile range as appropriate will be provided for continuous variables when performing descriptive analysis of continuous data.

Patients will be divided according to the mean of disease duration groups (below and above mean) and unadjusted comparisons between groups of the covariates and they will be evaluated using appropriate tests: chi-squared test will be used for categorical variables, t-test will be used for continuous variables, and the Kruskal-Wallis test for non-parametric variables; p-values will be generated.

We will determine the effect of early referral on the biologic treatment response patients with AS a multivariate analysis by using a stepwise linear regression model. The response variable is defined as BASFI and BASDAI at last visit. The baseline variables are considered demographic data, disease duration (years), methotrexate (yes/no), Current steroid therapy (yes/no), baseline BASFI, BASDAI, HLA-B27 positive (yes/no), anti-CCP (yes/no), present smoking (yes/no).

We will determine the effect of early response by using the difference in change between the baseline of BASDAI and BASFI and last follow-up. P-value <0.05 will be considered statistically significant.

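### One null hypothesis is tested on two primary outcomes at p<0.05 with no decision rule or correction, so under an either/or reading the false-positive rate exceeds 5%

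*Combined protocol and SAP*

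**What the plan says.** The Hypothesis paragraph in Section 8.2 gives one null: "There is no difference in response between early and delayed referral to biological treatment". Section 8.3 attaches two primary outcomes to it: "Primary Outcomes: Disease activity Index BASFI and BASDAI from the last follow-up visit".

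Section 8.6 describes two analyses that bear on the hypothesis. The first is a stepwise linear regression: "The response variable is defined as BASFI and BASDAI at last visit". Disease duration in years and the baseline scores are among its candidate variables. The second evaluates an effect "using the difference in change between the baseline of BASDAI and BASFI and last follow-up"; no test is named for it. The section closes with "P-value <0.05 will be considered statistically significant".

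No section ranks the two outcomes, names a main analysis, says whether one or both outcomes must be significant, or adjusts for multiple tests. Sidedness is not stated. Section 8.4 adds: "There is no pre-identified study size".

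**The concern.** The plan is not labelled exploratory. It states a hypothesis, separates primary from secondary objectives, names primary outcomes and fixes a significance threshold. A reader will therefore take 0.05 as the error rate of its conclusion about early versus delayed treatment.

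That holds only if one prespecified test carries the conclusion, or if both outcomes must succeed. The text also permits a third rule, under which a significant result on either BASDAI or BASFI is reported as rejecting the null. Under that rule 0.05 applies to each test and the error rate of the conclusion is higher. If the change-from-baseline comparison is a further separate test of each score, up to four results could be used in this way.

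**Working it through.** **Inputs from the documents.** Threshold 0.05 per test (Section 8.6); two primary outcomes (Section 8.3); one null of no difference (Section 8.2), which I read as two-sided. The documents give no sample size, effect size, standard deviation, correlation or familywise error rate. The only figure to reproduce is the single-test level: 1 - 0.95 = 0.05.

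**Assumptions.** 200 patients, two equal groups, BASDAI-BASFI correlation 0.3-0.8, baseline to last-visit correlation (ρ) 0.3-0.5. Analysis of covariance (ANCOVA) on the last-visit score stands in for the stepwise regression, and an unadjusted t-test is used for change.

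**Step 1: independent tests, as a limit.**
- Either direction, two tests: 1 - 0.95² = 9.75%. Four tests: 1 - 0.95⁴ = 18.5%.
- Favouring early only, where each two-sided test contributes 0.025: 1 - 0.975² = 4.9%, and 1 - 0.975⁴ = 9.6%. One test gives 2.5%.

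**Step 2: simulated null trials under the assumptions above.**

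| Tests that may reject the null | Any false difference | False result favouring early |
|---|---|---|
| One | 5% | 2.5% |
| Two (last visit) | 7.1-10.1% | 3.3-5.4% |
| Four (change t-tests added) | 10.9-15.7% | 5.1-8.2% |

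The ends of these ranges include simulation noise; the upper end for two tests, for example, slightly exceeds the 9.75% limit.

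**Step 3: cross-check with correlated normal test statistics.** Let r be the correlation between the BASDAI and BASFI tests, and s the correlation between the two analyses of one score. With equal variances at baseline and last visit, the ANCOVA and change-score statistics correlate at s = √((1+ρ)/2). That is √0.65 = 0.81 for ρ = 0.3 and √0.75 = 0.87 for ρ = 0.5. The nearest settings calculated (500,000 draws each) were:
- Two tests: 9.6% at r = 0.3 and 7.8% at r = 0.8; favouring early, 4.8% and 3.9%.
- Four tests: 14.6% at r = 0.3, s = 0.8 and 10.8% at r = 0.8, s = 0.9; favouring early, 7.3% and 5.4%.

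These lie inside the ranges in Step 2. Even at r = 0.9, two tests give 7.0%.

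**Step 4: effect of a correction.** With Holm's procedure on the two ANCOVA tests, a false rejection needs at least one p-value below 0.025 when both nulls are true. The bound is 2 × 0.025 = 5% whatever the correlation; simulation gave 4.2-4.7%.

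**Step 5: cost in power.** A test with 80% power at two-sided 0.05 has noncentrality 1.960 + 0.842 = 2.80. Against the 0.025 critical value of 2.241, power is Φ(2.80 - 2.241) = Φ(0.56) = 71%.

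**The case against.** **The plan never says that either outcome suffices.** This is correct. If both outcomes had to be significant in one designated analysis, the error rate would be at most 5% (0.6-2.2% in simulation). The firm criticism is that the rule is missing; the inflation is conditional on an either/or reading.

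**Four tests is only one reading.** The change sentence names no test and does not say that the duration groups are compared. If change is regressed on disease duration with its own baseline score and the same covariates, then subtracting the baseline B from both sides of Y = α + βD + γB gives Y - B = α + βD + (γ - 1)B. The duration coefficient β and its p-value are unchanged, so nothing is added. The 11-16% range needs separate unadjusted change tests. The two-test range does not.

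**The simulation is not the planned model.** This also stands. Stepwise selection may drop the baseline score or disease duration, the mean split need not give equal groups, and neither feature was modelled. The true rates could differ from those shown.

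**The objectives might supply an order.** Section 8.1 separates a primary objective (clinical impact of early referral) from a secondary one (response to biological treatment), and Section 8.5 refers to primary and secondary endpoints. Neither is mapped to a score or a test, so no order follows.

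**Two stronger inferences are not supported.** A reader might take 7-10% or 11-16% as the chance of falsely concluding that early treatment is better. With two-sided tests about half of false positives point the other way, so the relevant figures are 3-5% and 5-8%, against 2.5%. A reader might also infer that the testing plan was settled after the data were seen, because version 3.0 (29 July 2021) postdates the planned end of data collection (01 October 2020). Section 4 lists only administrative amendments (milestones and spelling), and the documents do not date the first version, so they do not establish this.

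**Conclusion.** The concern holds in a conditional form. The plan leaves the decision rule for two primary outcomes unspecified and makes no correction. If either outcome may reject the null, the chance of at least one false significant difference is roughly 1.4 to 2 times the nominal 5% (7/5 to 10/5) for the last-visit tests alone. Separate unadjusted change tests would take it to roughly 2 to 3 times (11/5 to 16/5). The exact size rests on the assumed sample size, grouping, correlations and substitute model. That the rate exceeds 5% under the either/or rule does not depend on one particular correlation: it persists at every value examined, up to 0.9. This should be corrected, because no other part of the plan fixes which result carries the conclusion.

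**What to change.** In Section 8.6:

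1. Name the last-visit early-versus-delayed effects on BASDAI and BASFI as the only two confirmatory tests, and state that they are two-sided.
2. Estimate them from a prespecified linear model that always keeps the disease-duration (early/delayed) term and the baseline score. State the form of that term and the other covariates in advance. Do not leave these to stepwise selection, since Holm's 5% guarantee needs valid p-values from a fixed model.
3. Apply Holm's procedure: the smaller p-value against 0.025 and, if that passes, the larger against 0.05.
4. Report change-from-baseline comparisons as supportive estimates with 95% confidence intervals and no significance claim.

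Requiring both outcomes to be significant, or designating a single primary outcome, would also control the error. Holm is suggested because it lets either outcome succeed.

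The cost is more than a multiplicity sentence, because the confirmatory model replaces the stepwise one. It needs no data beyond those already listed in the plan. The statistical price is at the first step, where 80% power falls to about 71%; the second test, if reached, keeps the 0.05 level.

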### **8.4. Study Size**

There is no pre-identified study size. All patients that meet the inclusion/exclusion criteria will be entered into the study.

### **8.5. Data Management**

The study data is structured data and will be exported into an excel spreadsheet. The rheumatology center in Baghdad Teaching Hospital will analyze the data and provide it with results based on the defined primary and secondary endpoints.

